- SAE monitoring: a final chart review for monitoring SAEs should be completed approximately 30 days after the completion of the 18 month visit. If an SAE is identified a final SAE form will be submitted to PPCSPCC and CIRB as required.
- All CRFs should be completed and submitted to PPCSPCC.

XI. DOG REMOVALS

- **Removal and replacement of the study dog.**

Pairings between Service Dogs/Emotional Support Dogs and study participants may fail because a bond is not established between them. Vendors are experts at matching human and animal personalities to limit the possibility that this will happen. Based on information from vendors, a bonding failure will usually occur within the first two weeks after returning home with a dog. In the case of failed bonding, a VA Dog Trainer will intervene and inform a Contracting Officer's Representative (COR), who will inform the vendor. Dogs may also develop disqualifying health or behavioral problems at any time after pairing that disrupts the pairing process. In other cases the bonding relationship may be interrupted due to short term absences by the participant (i.e., hospitalization, transitional housing, etc.) or due to the death of the original study dog in which a replacement dog may be sought.

If issues are identified that require the removal of a study dog, site staff will inform their local LSI. The LSI will work with the study Chair, the National Dog Trainer, and other leadership as needed to determine whether the dog should be temporarily or permanently removed. If the decision to temporarily remove the dog is agreed upon, the research team will assess the procedure for determining when and what constitutes resolution of the extenuating circumstances and when it would be appropriate to return the dog or offer a replacement dog.

Study leadership will maintain ongoing communication during all temporary removals to monitor the situation. Should the circumstances surrounding the temporary removal of the dog not get resolved in a reasonable amount of time - as determined by study leadership - the study dog may be permanently removed. If the dog is permanently removed with no plan for a replacement dog, the participant may be asked to continue in the study to complete follow up visits (Intent to Treat). If the participant does not want to remain in the study they will be withdrawn.

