Participants who refuse follow-up visits or are not otherwise eligible (as determined by leadership) will be asked to complete the Exit Interview during the permanent dog removal visit

or by phone within approximately 2 weeks of the permanent dog removal visit, or after the decision to permanently remove the dog has been made.

XII. STUDY WITHDRAWAL & TERMINATION

Circumstances surrounding the decision to withdraw a participant can vary from case to case. Early withdrawals that result from exclusionary criteria identified during the screening and baseline phases tend to be more straightforward and can be processed at the site level. Withdrawals that result from early termination of paired participants tend to involve more complex and varied circumstances that requires input from multiple members of the leadership team. Medical and scientific judgment should be exercised in deciding whether to terminate a participant from the study, especially once participants have been paired with a study dog. A case-by-case evaluation will be the standard approach to handling decisions to terminate participants from the study.

There are a number of reasons that a participant may be terminated/withdrawn from the study. These include:

- a. Safety concerns: the research team find out it is not safe for the participant to remain in the study. For example, the participant's health worsens.
- b. Missed study appointments: Participants do not keep scheduled study visits.
- c. Lost to follow-up: Participants do not respond to research staff attempts to contact them by phone or mail.
- d. Participant's home is inaccessible to the research team: a participant moves to a home that is not accessible to the research team, their existing home becomes inaccessible to the research team, or they move out of the study area.
- e. Deployment.
- f. Personal choice: participant decides for any reason that they no longer want to take part in the study, or they decide to return your dog or withdraw their study consent.
- g. Dog mistreatment: There is evidence that the dog has been physically or psychologically abused or mistreated. Signs of mistreatment include evidence that the dog:
 - has been hit or kicked (cowering, shaking, head shyness in the presence of the participant or a family member)
 - has been tied to an object outside
 - is fearful e.g. the dog stays away from the participant or a family member
 - has lost weight but does not have a medical condition that explains why

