- Paired participants who have been terminated early from the study should be provided with a withdrawal letter at the participant's last visit. If the participant refuses the letter or staff is not able to provide the participant with the letter at the time of the final visit these reasons should be documented and the letter filed in the participant study record.
- If applicable, the Exit Interview should be administered to the participant prior to officially withdrawing the participant early from the study. Participants will receive \$10 for their voluntary completion of this interview.
- A final chart review for monitoring of SAEs should be completed approximately 30 days after the decision to withdraw/terminate the participant from the study has been made. If an SAE is identified the final SAE form will be submitted to PPCSPCC and CIRB as required.
- CPRS record must be updated.
- If a HIPAA revocation form is signed, a copy should be submitted to CSP and the original filed locally with the consent, an addendum note in CPRS regarding the revocation process should be submitted, and the study termination form (form 24) updated to reflect this process.
- All CRFs must be completed and submitted to PPCSPCC.

XIII. MONITORING AND REPORTING ADVERSE EVENTS

- **Importance of Adverse Event Reporting**

Timely and complete reporting of safety information assists study management in identifying any untoward medical occurrence, thereby allowing: a) protection of safety of study participants, b) a greater understanding of the overall safety profile of the study treatments and therapeutic modalities, c) improvements in study design or procedures, and d) compliance with regulatory requirements.

- **Role of the Site Investigator in Adverse Event Monitoring**

The site investigator will be responsible for the adverse event reporting requirements as outlined below:

- Reviewing the accuracy and completeness of all adverse events (AE) reported.
- Compliance with VA CIRB policies for reporting AEs and/or serious adverse events (SAEs) (see VHA Handbook 1058.01 and CIRB website for details)
- Closely monitoring research participants at each study visit for any new SAEs.

- **Collection of Safety Information**

1. Adverse Events

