In order to detect a 10-point difference in treatment group mean scores for the WHO-DAS 2.0 over the 18 months of follow-up, at a statistical significance level of 0.05 (two-tailed test) and a power of 0.85, 32 participants per group will be needed (see Table 6). In order to detect a 15% difference in mean scores for MCS over the 18-months of follow-up, at a statistical significance level of 0.05 (two tailed test) and a power of 0.85, 82 participants per group will be needed (see Table 6). In order to detect a 15% difference in mean scores for the PCS over the 18-months of follow-up, at a statistical significance level of 0.05 (two tailed test) and a power of 0.85, 60 participants per group will be needed (see Table 6). The sample size estimates were obtained using the PC-software SAS 9.2.

Assuming the largest of the three sample sizes, 82 participants per group, and a maximum of 25% participant loss or dropout rate a sample size of 110 participants per treatment will be required for this study. To obtain the necessary sample size of 220 participants, at least three VA medical centers will be recruited. Once a participant has been determined to be eligible for the study at the participating VA medical center, randomization to one of the two groups will be accomplished by a telephone call to the Perry Point Coordinating Center. All sites will be encouraged to recruit and enroll participants faster than the stated requirements.

- **Statistical Methods**

The intent-to-treat population (ITT) is defined as the population of participants who will be randomized in either the Service Dog (SERV) or Emotional Support Dog (EMOT) treatment groups. The participants will be categorized based on their initial randomized group assignment and will be included in analyses irrespective of their status – completer or drop out of the study before completion. A per protocol population (PP) is defined as the population of participants who are paired with a dog. Analyses of all outcome measures – primary and secondary – will use both the ITT and PP population.

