### 3.7 Follow-up

The primary objective of this study is to determine how the provision of a Service Dog or an Emotional Support Dog impacts function and quality of life for Veterans with PTSD. Primarily, the objective is to compare functioning and quality of life change, relative to baseline, over the 18-month intervention period between the two groups of Veterans with PTSD, i.e., those who receive Service Dogs and those who receive Emotional Support Dogs. The secondary outcomes in this study are: 1) a reduction in PTSD symptoms as measured by the PTSD Civilian Checklist (PCL); 2) improvement in depression as measured by the PHQ-9; 3) improvement in sleep as measured by the Pittsburg Sleep Quality Index (PSQI); 4) decreased thoughts of suicide as measured by the Columbia-Suicide Severity Rating Scale (C-SSRS); and 5) to characterize and compare how healthcare costs and utilization are impacted. All primary and secondary outcome measures will be collected at baseline, clearing, and at 3, 6, 9, 12, 15 and 18 month post-pairing. The following forms will be used during the follow-up phase of the study.

Table 2. Follow-up Phase Data Forms

Form #	FORM Name	1 week	2 week	1 month	2 month	3 month	6 month	9 month	12 month	15 month	18 month
	PHASE	2	2	3	3	3	3	3	3	3	3
	VISIT #	01	02	01	02	03	06	09	12	15	18
	LOCATION	Home	H/P	Home	H/P	Clinic	Home	Clinic	Home	Clinic	Home
3	CAPS										R
7	WHO-DAS 2.0					R	R	R	R	R	R
8	PCL-5					R	R	R	R	R	R
9	PSQI					R	R	R	R	R	R
10	VR-12					R	R	R	R	R	R
11	C-SSRS					R	R	R	R	R	R
12	PHQ-9					R	R	R	R	R	R
13	DAR					R	R	R	R	R	R
14	HERC Non-VA Utilization					R	R	R	R	R	R
15	WPAI: GHP v2.0					R	R	R	R	R	R
17	Medication Log	A	A	A	A	A	A	A	A	A	R
18	Payment Log	A	A	A	A	A	A	A	A	A	R
19	Post Pairing Evaluation	R	A	A	A	A	A	A	A	A	A
20	Veteran and Service/ES Dog Visit Report	R	A	R	A	A	R	A	R	A	R
21	Dog Related Questions	R	R	R	R	R	R	R	R	R	R
22	Dog Return	A	A	A	A	A	A	A	A	A	A
23	Veterinarian Checklist	R					R		R		R
24	Study Completion/Termination	A	A	A	A	A	A	A	A	A	R
24a/b	Exit Interview – SERV or Exit Interview – EMOT										R
24c	Dog Trainer Evaluation										R
25	Protocol Deviation	A	A	A	A	A	A	A	A	A	A
26	Adverse Events	A	A	A	A	A	A	A	A	A	A
26a	Adverse Events for Dogs	A	A	A	A	A	A	A	A	A	A
27	Serious Adverse Events	A	A	A	A	A	A	A	A	A	A
27a	Serious Adverse Events for Dogs	A	A	A	A	A	A	A	A	A	A
28	AE/SAE Follow-up	A	A	A	A	A	A	A	A	A	A
28a	SAE Follow-up for Dogs	A	A	A	A	A	A	A	A	A	A

H/P = HOME/PHONE

R = REQUIRED

A = AS NEEDED

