### 3.8 Sample Size

The goal for this study is a sample size of 220 including adjustment for subjects who withdraw or are lost-to-follow-up and interim analyses. In order to detect a 15% difference in mean scores for MCS (outcome requiring largest sample) over the 18-months of follow-up, at a statistical significance level of 0.05 (two-tailed test) and a power of 0.85, 82 participants per group will be needed, and 110 participants per treatment (220 total) will be required to account for a maximum of 25% post-pairing participant loss or dropout rate (see protocol). This sample size results in an expectation of 110 subjects in each of the treatment groups. For challenges in the recruitment of participants or in the pairing (or availability) of dogs, sample size will be revisited and adjusted accordingly taking into account the study's post-pairing termination rate. For 80%, a sample size of 72 per group is needed, and 90 participants per treatment (180 total) to account for a 20% post-pairing termination rate or 85 (170) to account for a 15% termination rate. When such challenges occur, a sample size of 180 will be the aim.

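### No primary outcome is scheduled at exit for paired Veterans who leave early, so those leaving before month 3 have no post-pairing WHO-DAS 2.0 or VR-12 score

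*Protocol*

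**What the plan says.** **Schedule.** Protocol Table 5 gives WHO-DAS 2.0 and VR-12 at Baseline 1, Baseline 2 and months 3, 6, 9, 12, 15 and 18. SAP 3.7 agrees: "All primary and secondary outcome measures will be collected at baseline, clearing, and at 3, 6, 9, 12, 15 and 18 month post-pairing". SAP Table 2 allows the termination and dog-return forms at any visit, but has no early-exit column for an outcome instrument.

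**Early withdrawal or termination.** Protocol XII.4 lists a withdrawal letter, a safety chart review about 30 days later, record and privacy steps, submission of case report forms, and this: "If applicable, the Exit Interview should be administered to the participant prior to officially withdrawing the participant early from the study". The requirement to complete all forms adds no outcome score, because none is scheduled at that point.

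**Permanent removal without follow-up.** Protocol XI says: "Participants who refuse follow-up visits or are not otherwise eligible (as determined by leadership) will be asked to complete the Exit Interview".

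**Timing of failure.** Protocol XI reports from vendors that "a bonding failure will usually occur within the first two weeks after returning home with a dog". It adds that health or behavioural problems in the dog can arise at any time. Under the rules on children in the home, trainer visits at weeks 1 and 2 and months 1 and 2 can lead to removal of the dog and termination of the Veteran.

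**Analysis.** SAP 5.3 analyses the data as observed. If missing data are judged substantial, it adds multiple imputation under missing at random and, as needed, pattern-mixture models under missing not at random.

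**The concern.** A Veteran who leaves in the first weeks after pairing may well differ from one who stays, and the difference may concern the outcome itself. The study usually still has a contact with that Veteran, because the dog must be returned and an interview is offered, but it does not ask for the primary outcomes then. A mixed model on observed data in effect fills in early leavers from similar Veterans who remained. If leaving is related to outcome and differs by arm, the comparison can be biased, and nothing recorded after pairing would show by how much.

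**Working it through.** **1. Which routes lose the outcome visits**

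| After pairing | Outcome visits (WHO-DAS 2.0, VR-12) | Source |
|---|---|---|
| Temporary removal | Continue, in clinic | Protocol XI |
| Replacement dog | Continue on the existing schedule | Protocol XI |
| Permanent removal, Veteran agrees and is allowed to stay | All continue, in clinic | Protocol XI |
| Dog dies, Veteran willing | Continue on the same timeline | Protocol XIII, Risks to subject |
| Permanent removal, follow-up refused or denied | None; Exit Interview sought | Protocol XI |
| Early withdrawal or termination | None; Exit Interview if applicable | Protocol XII.4 |
| Child-safety termination | No follow-up option stated in that section | Safety Monitoring of Children in the Home |

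Only the last three rows have the gap.

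**2. What these leavers contribute**

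- Leaving before month 3: two pre-pairing scores (Baseline 1 and Baseline 2) and no post-pairing score.
- Leaving later: the last score can predate the exit by up to about three months, the spacing of the visits.
- In a pattern-mixture model, the pattern that ends before month 3 has no post-pairing data. Whatever identifying restriction is chosen, its whole post-pairing distribution is borrowed from other patterns.

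**3. Is it a sample-size problem?**

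The plan's figures reproduce. Inputs, from Protocol XVIII (Sample Size) and Table 6:

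- Target: "In order to detect a 15% difference in mean scores for MCS over the 18-months of follow-up". With the Emotional Support Dog mean of 33.2, the difference is 0.15 × 33.2 = 4.98; the SD is 10.6.
- Error rates: "a statistical significance level of 0.05 (two tailed test) and a power of 0.85, 82 participants per group will be needed".
- Loss: "a maximum of 25% participant loss or dropout rate a sample size of 110 participants per treatment will be required".

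n = 2(1.960 + 1.036)² × 10.6² / 4.98² = 81.4, so 82 per group. Then 82 / (1 − 0.25) = 109.3, so 110 per group.

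Power for MCS with 110 enrolled per group is 93.6% at no loss, 91.1% at 10% loss and 85.5% at 25% loss. Early leavers within the allowance (0.25 × 220 = 55, covering every kind of loss) do not break the stated power.

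**4. Can the bias be sized?**

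Take the month-18 WHO-DAS 2.0 difference, Service Dog minus Emotional Support Dog (negative favours Service Dogs). Suppose the model predicts leavers exactly as if they had stayed. Then

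true difference = model difference + (p_S × w_S − p_E × w_E),

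where p is the share leaving in each arm and w is how much worse leavers really are than predicted. The documents give neither p nor w. The values below are assumptions with no source in the documents, shown only to display the spread. The model difference is set at −5. For failed Service Dog Veterans, w_S is the worsening alone if the 5-point benefit persists after losing the dog, and the worsening plus 5 if it is lost.

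| Leaving, Service vs Emotional Support | Worsening | Truth if benefit persists | Truth if benefit is lost |
|---|---|---|---|
| 25% vs 15% | 8 | −5 + (2.0 − 1.2) = −4.2 | −5 + (3.25 − 1.2) = −2.95 |
| 30% vs 10% | 13 | −5 + (3.9 − 1.3) = −2.4 | −5 + (5.4 − 1.3) = −0.9 |
| 25% vs 25% | 13 | −5 + (3.25 − 3.25) = −5.0 | −5 + (4.5 − 3.25) = −3.75 |
| 15% vs 25% | 8 | −5 + (1.2 − 2.0) = −5.8 | −5 + (1.95 − 2.0) = −5.05 |

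The estimate of −5 may overstate, match or understate the truth. Even equal leaving is free of bias only if the benefit outlasts the dog. The calculation also presumes that outcomes after leaving belong to the target of estimation, which the SAP does not say.

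**The case against.** The strongest counter-argument is that the protocol already works to keep outcome data. Removal of a dog does not end follow-up: Veterans are encouraged to complete all assessments and are paid for clinic visits. A reader might infer from the timing of bonding failure that most failed pairings leave no outcome. The documents do not support that. The two-week remark concerns bonding failure only, which leads first to trainer help and possibly to a replacement dog, with outcome visits continuing. Other failures can come at any time, and no rate of exit before month 3 is given. This part of the objection stands and confines the point to leavers. It does not remove it, because staying on after permanent removal is discretionary and the exit routes remain.

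Scores after replacement are a separate matter: they are collected, but SAP 5.3 keeps them out of the primary analysis. An exit form would not change that.

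SAP 5.3 also already names tools for informative dropout. That is a real safeguard, but it is conditional on missing data being judged substantial, and for exits before month 3 it would run on assumption alone.

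Finally, an exit score is imperfect. Veterans who have died, been deployed or been lost to contact cannot give one, and some will refuse. Distress at removal may be short-lived. WHO-DAS 2.0 looks back 30 days, so at two weeks 16 of those days precede the pairing date. The Exit Interview may be by phone, while both instruments are paper forms. These limits stand, and they are why the score belongs in sensitivity analyses.

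**Conclusion.** The gap is confirmed for one group: paired Veterans withdrawn or terminated early, or refusing or denied follow-up after permanent removal. None has a primary outcome scheduled at exit, and those who go before month 3 have no post-pairing primary outcome at all.

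Two further inferences are not supported. Loss within the 25% allowance does not undermine the stated power. Nor can one say that the result is biased by a given amount or towards a given arm: that needs exit rates by arm, leavers' outcomes, and whether benefit persists after the dog is gone, and the documents give none of these.

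This is a modest design improvement. Its value is that it gives the planned sensitivity analyses some data on leavers. It rests on the assumption that a useful share of leavers can be reached and are willing.

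**What to change.** In Protocol XI (permanent removal), Protocol XII.4 and SAP Table 2, offer WHO-DAS 2.0 and VR-12 to every reachable, willing paired Veteran leaving early, before the Exit Interview. If the contact is by phone, mail the forms or read them aloud, and record the mode.

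Record the actual date relative to pairing and to dog removal. Keep the as-observed primary analysis as planned. Use the exit scores in a sensitivity analysis at their actual times, and to inform the pattern-mixture models. Report how many leavers gave a score, by arm.

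The cost is 10 to 15 minutes for WHO-DAS 2.0 plus about 5 for VR-12, so 15 to 20 minutes of self-completed forms. For early withdrawals, XII.4 already pays $10 for the interview contact. It needs a minor amendment and some mailing or reading aloud, but no new visit. The drawbacks are refusals, scores coloured by short-term distress, recall that partly predates pairing for very early exits, and mixed modes of completion.
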